7.5 Future Use of Study Data

Information redacted due to confidential content

8.0 Risk Analysis and Risk Assessment

8.1 Risks and Foreseeable Adverse Device Effects

Information redacted. Please refer to the Instructions for Use

8.2 Methods to Minimize Risks

The device design, non-clinical testing, clinical study design, and the Instructions for Use are intended to minimize the risks associated with the endovascular procedures.

9.0 Safety Monitoring and Event Reporting

9.1 Data Safety Monitoring Board

A Data Safety Monitoring Board (DSMB) consisting of independent physicians, who are not investigators in the investigation, nor have a perceived conflict of interest with the conduct and administration of the investigation, will be convened on a regular basis to evaluate investigation progress and review adverse events.

9.2 Clinical Events Committee

An independent Clinical Events Committee (CEC) consisting of physicians, who are not investigators in the investigation, nor have a perceived conflict of interest with the conduct and administration of the investigation, will be established to adjudicate clinical events reported during the investigation. This adjudication will be performed according to standard operating procedures to assess whether the events were due to a pre-existing or unrelated condition, procedure-related, technique-related, and/or device-related.

Regularly scheduled review/monitoring of all patient data will be conducted at the Data Coordinating Center, in part, for identification of adverse events and assurance that they are correctly reported to the DSMB and CEC.

9.3 Adverse Event Reporting

Events known to be related to pre-existing conditions or existing at admission are not considered adverse events (e.g., prior medically-treated cardiac arrhythmia with no change in status during the endovascular procedure). Additionally, common standard of care practices are not considered adverse events (e.g., centers located at high geographical altitudes that discharge all patients on home oxygen therapy regardless of procedure).

All adverse events (i.e., device-related and non-device-related) are to be reported using the appropriate case report form (Adverse Event/Complication form). In cases of adverse device effects (adverse event with relation to the study device) or serious adverse events, completed forms should be submitted to the Data Coordinating Center immediately upon knowledge of the event.

Cook Research Incorporated
[name]

[name]
[contact]
[contact]

The Data Coordinating Center will notify the sponsor accordingly. In accordance with applicable requirements, the investigator will notify the local Ethics Committee/IRB, while the sponsor will notify the regulatory authority. Furthermore, if the sponsor determines that the device presents a potential risk to the study patients, all investigators in the study will be notified. Refer to section 8.1 for a list of potential adverse events related to this study.

10.0 Administrative

10.1 Data Collection

Patient data will be collected and entered by the investigative site into an electronic case report form (eCRF) system. This is a secure, web-based system, allowing those with permission to access data from any location at any time. Data will be entered by qualified site personnel. Site personnel are required to have unique login names and passwords in order to enter patient data, and, in accordance with 21 CFR Part 11, the eCRF system creates a secure, computer-generated, time stamped audit trail to record the date and time of operator entries and actions that create, modify, or delete electronic records.

10.1.1 Data Archiving

Patient data and documents pertaining to the study are to be kept for the longest time required by the regulatory bodies overseeing the study. Archiving will be done in such a way that the data are not lost during this period. Both investigators and sponsor are obliged to keep the documents.

10.1.2 Data Protection

Each patient will be assigned a unique enrollment number, and will be identified to the sponsor only by this unique enrollment number and patient initials. While monitors necessarily will have access to protected health information, all monitors will have

appropriate training and follow procedures for proper handling of patient-identified information. Furthermore, whenever feasible, de-identified health information will be used by researchers involved in the study. “Researchers” include the patient’s physician and the staff of collaborators, investigators in other locations studying this device, the sponsor, and the companies or individuals with research responsibilities delegated by the sponsor.

These data may be used to gain additional experience with this device and to advance medical knowledge through presentations and articles regarding the study. These data may also be reviewed by government agencies that oversee research and may approve medical devices for commercial use.

These data may also be combined with health information about other patients. The sponsor or their designee will keep the data in an ongoing database of information about the Zenith® Dissection Endovascular System, so that information can be studied and analyzed. When the follow-up period is complete, no new information about individual patients will be added, but review of the data may continue. Presentations, reports, and articles about this investigation will contain only de-identified information.

10.1.3 Data Protection Agency

If applicable, the Danish Data Protection Agency will be notified about this investigation to conform with The European Act on Processing of Personal Data (Act No 429 of May 31, 2000) which entered into force on July 1, 2000, and which implements the Directive 95/46/EC on the protection of individuals with regard to the processing of personal data and on the free movement of such data.

10.2 Data Reporting

Progress reports and a final report at the conclusion of the clinical investigation will be submitted by the investigators and sponsor to the Ethics Committees and regulatory bodies as required by local regulations.

10.3 Emergency Situations and Vulnerable Subjects

Patients will not be treated with the Zenith® Dissection Endovascular System in emergency situations where prior consent of the patient or the patient's legally-authorized representative in accordance with 21 CFR Part 50 is not possible.

10.4 Criteria and Procedures for Withdrawal

The investigator must make a reasonable effort to ascertain and record the reason for withdrawal or discontinuation for each patient while fully respecting the subject's rights. The reasons for withdrawal and discontinuation of any patient from the investigation shall be recorded. If such discontinuation is because of problems with safety or lack of effectiveness, that patient shall still be followed-up in the investigation, if possible.

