5.6 Point of Enrollment

Point of enrollment will be based on the intent-to-treat population, and is defined to include any patient for whom the treatment procedure is initiated. More specifically, once a procedure has begun (i.e., cutdown or percutaneous access initiated), the patient would be included in the intent-to-treat population. The patient's informed consent will be obtained and assessment of the patient's conformance to the inclusion/exclusion criteria will occur prior to the procedure.

Study results will also be analyzed with respect to the consented patient population (i.e., all patients who gave consent to participate in the study, regardless of treatment).

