6.10 Criteria and Procedures for Study Termination

A patient's follow-up in the study will end after:

- 1) Failure to deploy the device + 30 days;
- 2) Conversion to open surgical repair + 30 days;
- 3) Patient withdrawal;
- 4) Patient death;
- 5) Closure of the investigation; or
- 6) Completion of all scheduled clinical and imaging visits through 5 years.

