7.4 Missing Data

Missing data will be addressed using three primary strategies: 1) estimating missing data with the best available data, 2) case deletion, and 3) multiple imputation.

The first strategy may be used for missing imaging data. Previous clinical trial experience suggests that some portion of the imaging data may not meet the criteria for accurate measurements by the core laboratory. However, it is recognized that the treating physician uses this information to provide the best possible care for the patient.

Therefore, it is reasonable to substitute any missing core laboratory measurements with the corresponding measurements made by the treating physician (or their staff). In addition, the absence or presence of clinical sequelae may provide the required missing

core laboratory assessment of device performance. Furthermore, imaging at subsequent time points may be available, making it possible to infer patient status at the time point of interest. This strategy is a best approximation of the missing data value.

The second strategy is case deletion. If the amount of missing data does not result in a reduction of analyzable patients to a number that is below that required for sufficient statistical power of the primary endpoints, then case deletion will be the method of choice for that analysis.

The third method is multiple imputation. This method will be used to predict missing endpoint or covariate data. It may be that the primary study endpoints may depend upon certain covariates. Therefore, it may be possible to model study endpoints, given a series of related covariates. This model-based imputation exercise may provide estimates of the missing data that can be utilized in estimating event rates and confidence bounds.

Strategies originating from Schafer⁴ will be used, supplemented with notes provided by Schafer.⁵ The computations will be performed using PROC MI and PROC MIANALYZE in SAS version 9.1 or later, or WinBUGS 1.4 or later.

Additional analyses of missing data may be performed as appropriate, including a tipping point analysis and a worst-case analysis.

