10.6 Early Termination or Suspension of the Investigation

The sponsor reserves the right to terminate/suspend the study at any point should they believe that important harmful events might result from its continuation. Subjects may withdraw from the study at any time without penalty or loss of benefits. The investigator may also decide to withdraw a subject from the study at any time on the basis of medical judgement. In any case, the reasons for withdrawal will be documented, when available.

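### The rules on follow-up after withdrawal (Sections 6.10, 10.4, 10.6) are not reconciled, and default case deletion in Section 7.4 can then drop day-30 outcomes that are not missing at random

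*Combined protocol and SAP*

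**What the plan says.** - **Section 6.10** lists the events that close a patient's follow-up: "A patient's follow-up in the study will end after" is followed by six items. Item 1 is "Failure to deploy the device + 30 days", and item 2 (open conversion) has the same 30-day extension. Item 3 is "Patient withdrawal", with no extension, no exception and no reference to Section 10.4.
- **Section 10.4** deals with withdrawal and discontinuation together, both from the investigation. Where discontinuation is for safety problems or lack of effectiveness, "that patient shall still be followed-up in the investigation, if possible".
- **Section 10.6** adds: "The investigator may also decide to withdraw a subject from the study at any time on the basis of medical judgement". Section 5.1 states that the study is not blinded.
- **Section 7.4** says that, provided the analyzable number stays large enough for power, "case deletion will be the method of choice for that analysis". It also names multiple imputation. Sensitivity work is optional: "Additional analyses of missing data may be performed as appropriate, including a tipping point analysis and a worst-case analysis".
- **Section 5.6** says that once the procedure has begun "the patient would be included in the intent-to-treat population". It does not say how a patient with unknown day-30 status is counted.
- **Section 7.1** tests 67 patients, with 60 needed for safety and 40 for effectiveness. Withdrawal and loss to follow-up are mentioned as reasons for extra enrollment, but no rate is given.

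**The concern.** Both primary endpoints are day-30 proportions compared with fixed performance goals. There is no control arm in which the same losses would partly cancel, so anything that removes failures from the denominator moves the result directly toward success.

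The plan allows this by following its own rules. A patient can be withdrawn before day 30 by own choice or on an investigator's judgement. It is unclear whether that patient's follow-up then stops (Section 6.10) or continues where feasible (Section 10.4). If it stops, day-30 status is missing, and the default handling is to delete the patient. Patients who leave because of a safety problem, or on medical judgement, are plausibly at higher risk than those who stay, so the deletion need not be neutral. The two 30-day extensions in Section 6.10 show that the authors saw the need to reach day 30 after failed deployment and open conversion. Withdrawal has no equivalent.

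**Working it through.** **Inputs.** From Sections 3.3 and 7.1: one-sided exact binomial test at 0.025; safety goal p0 = 0.512 and expected rate p1 = 0.692; survival goal p0 = 0.794 and expected rate p1 = 0.949; N = 67. The numbers of deleted patients and the deletion probabilities below are assumptions.

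**1. The plan's own figures.** The pass mark c(n) is the smallest c with P(X ≥ c | n, p0) ≤ 0.025, and power is P(X ≥ c(n) | n, p1).

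- Safety, n = 60: pass mark 39, type I error 0.0216, power 80.2%.
- Survival, n = 40: pass mark 37, type I error 0.0233, power 85.5%.
- At n = 67: pass marks 43 (safety, type I error 0.0220, power 84.7%) and 60 (survival, type I error 0.0223, power 98.0%).

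The stated 60 and 40 reproduce, so the sample sizes are not in question. Because case deletion is the default while the powered number remains, up to 67 − 60 = 7 patients can be deleted for safety and 67 − 40 = 27 for survival.

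**2. Which outcomes can go missing.**

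- An MAE or death recorded before withdrawal is an observed failure on that endpoint.
- Failed deployment and open conversion are followed for 30 more days.
- What remains is (a) an MAE or death after withdrawal but before day 30, and (b) day-30 survival for a patient withdrawn after an MAE.

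**3. Upper bound: every deleted patient is a failure.** The number of successes stays fixed while n falls.

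| Deleted | MAE-free | p | Decision | Survivors | p | Decision |
|---|---|---|---|---|---|---|
| 0 | 42/67 | 0.039 | fail | 59/67 | 0.048 | fail |
| 1 | 42/66 | 0.028 | fail | 59/66 | 0.0254 | fail |
| 2 | 42/65 | 0.020 | pass | 59/65 | 0.012 | pass |

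Both examples start one success short of the pass mark.

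**4. Type I error under an assumed deletion probability.** Let X ~ Bin(67, p0) be the successes. Each of the 67 − X failures is unseen and deleted with probability q, so D ~ Bin(67 − X, q). The trial passes if X ≥ c(67 − D). Summing exactly over X and D:

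| q (assumed) | Safety | Survival |
|---|---|---|
| 0 | 0.022 | 0.022 |
| 1% | 0.022 | 0.022 |
| 2% | 0.024 | 0.023 |
| 5% | 0.029 | 0.024 |
| 10% | 0.047 | 0.031 |

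At the performance goals, the expected number of deleted failures is 67 × 0.488 × q for safety (1.6 at 5%, 3.3 at 10%) and 67 × 0.206 × q for survival (0.7 and 1.4). No successes are deleted in this model, so it too leans toward the worst case.

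**The case against.** The sections can be read together. Item 3 of Section 6.10 most simply means the patient's own act, and Section 10.6 separates subjects who withdraw from investigators who withdraw them. Section 10.4 then works as a specific exception, qualified by feasibility and by the subject's rights. Failed deployment and open conversion, the clearest cases of device treatment stopping, are already followed for 30 days. Section 9.3 requires all adverse events to be reported, serious ones immediately, and Section 9.2 provides independent adjudication. Section 7.4 also offers multiple imputation. On this view only a cross-reference is missing.

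Much of this stands. A reader might infer that the sections flatly contradict each other, or that patients with early MAEs or deaths disappear from the analysis. The documents support neither: a coherent reading exists, and recorded events remain failures. But the text does not state that reading. Section 10.4 speaks of discontinuation from the investigation, which fits poorly with a meaning limited to stopping device treatment. On any reading, no passage says that a patient withdrawn by the investigator has day-30 status collected, or how unknown status is counted. Imputation is not the default, and the tipping-point and worst-case analyses are optional. The weakness of default deletion exists without the withdrawal wording. That wording adds a route by which the deleted patients may be the higher-risk ones.

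**Conclusion.** The concern holds as an unreconciled set of rules whose default handling can bias both primary rates upward. It should be corrected, but it does not show that the trial's error rate is in fact inflated.

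The size depends on assumptions. Two unseen failures, both deleted, are enough to reverse either decision when the result is one success short; one is not. With assumed deletion probabilities of 5% and 10% per failure, safety type I error is 0.029 and 0.047, and survival is 0.024 and 0.031. At 5% survival stays within 0.025, and at 1% or 2% both endpoints do. The study claim needs both nulls rejected, so its error is no larger than that of whichever endpoint sits at its goal.

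A reader might carry the bound to all seven deletions that the safety power rule permits, where the same calculation gives 0.153 for safety and 0.476 for survival. The documents do not support using those figures as an estimate: they give no withdrawal rate, and every deleted patient would have to be an unrecorded failure.

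**What to change.** 1. **Section 6.10, item 3:** limit it to withdrawal of consent by the patient, and cross-refer to Section 10.4.
2. **Sections 10.4 and 10.6:** state that withdrawal by the investigator, or for safety or effectiveness reasons, does not end collection of day-30 vital status and MAE status unless the patient withdraws consent.
3. **Section 7.4, primary endpoints:** replace case deletion with all 67 patients in both denominators, and count any MAE or death observed before withdrawal as a failure on the endpoint concerned. Prespecify one rule for unknown day-30 status, for example multiple imputation (stating how it combines with the exact test) or counting it as failure. Make the tipping-point analysis mandatory.

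**Cost.** Wording in four sections, some added follow-up and one further analysis. The 30-day clinical exam is already scheduled in Section 6.9, and the patient's right to withdraw is untouched. If unknown status counts as failure, power falls. With the remaining patients at the expected rates, safety power goes from 84.7% with no unknowns to 80.2% with one, 75.0% with two and 69.0% with three. Survival power goes from 98.0% to 94.9%, 88.7% and 77.3%. The loss is small only if unknowns are few, which is a further reason to obtain day-30 status.

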10.5 Deviations from Clinical Investigation Plan

Deviations or non-compliances will be recorded together with an explanation. Deviations shall be reported to the sponsor, regulatory authorities, and Ethics Committee/IRB as required.

10.6 Early Termination or Suspension of the Investigation

The sponsor reserves the right to terminate/suspend the study at any point should they believe that important harmful events might result from its continuation. Subjects may withdraw from the study at any time without penalty or loss of benefits. The investigator may also decide to withdraw a subject from the study at any time on the basis of medical judgement. In any case, the reasons for withdrawal will be documented, when available.

10.7 Limitations of the Investigation

This study is inherently limited by the number of patients who will be excluded due to general, medical, and anatomical exclusion criteria. Additional challenges to the study include the anticipated comorbidities, which may confound data analysis.

10.8 Publication Policy

Publication policy, rights and obligations for this investigation have been negotiated, detailed and defined in the Investigation Contractual Documents and Agreements with the Investigation Site and Investigators.

10.9 Approvals and Agreements

The sponsor, coordinating investigator (if applicable), and the principal clinical investigators for each site shall agree to this document and any modifications. A justification for any modifications will be documented. Approval and agreement will be indicated by signing and dating the appropriate document.

10.10 General Information

10.10.1 Sponsor

The Sponsor for this investigation is Cook Research Incorporated. See Appendix A for contact information.

10.10.2 Manufacturer

The Manufacturer for this investigation is William Cook Europe, ApS. See Appendix A for contact information.

10.10.3 Data Coordinating Center

The Data Coordinating Center for this investigation will be Cook Research Incorporated. See Appendix A for contact information.

10.10.4 Investigation Compliance

The investigation shall be performed according to the Declaration of Helsinki.

The investigator is responsible for obtaining approval of this clinical investigation by the relevant Ethics Committee/IRB. The sponsor must be provided with a copy of this approval before delivery of any study device. Furthermore, the investigator will ensure that local regulations concerning data protection are followed.

Cook Research Incorporated is certified with the U.S. Department of Commerce's Safe Harbor Privacy program for the transfer of clinical study data pertaining to residents of the European Union. The Safe Harbor Privacy Program, which is jointly sponsored by the Department of Commerce and the EU Commission, allows organizations to self-certify to privacy standards that are higher than those currently required in the United States.

The U.S. companies that participate in the Safe Harbor Privacy Program voluntarily agree to uphold seven Safe Harbor Privacy Principles: Notice, Choice/Consent, Onward Transfer, Access and Correction, Data Integrity, Security, and Enforcement.

Adherence to these Safe Harbor Privacy Principles may be limited to the extent required by any legal, governmental, national security or public interest obligation.

10.10.5 Investigators

A complete list of the coordinating clinical investigator, principal clinical investigators, and clinical investigators will be updated and maintained by the Data Coordinating Center. Updates will be sent to sites periodically.

10.10.6 Monitoring Arrangements

The monitor for this investigation will be Cook Research Incorporated. See Appendix A for contact information.

The investigation will be monitored in accordance with written standard operating procedures consistent with applicable regulations. Written procedures for monitoring the investigation are maintained by the monitors and can be found in Appendix B.

10.10.7 Insurance

The devices are covered by sponsor's product liability insurance with Chubb Group of Insurance Companies, and a clinical study insurance policy will be taken out according to local requirements. A copy of the insurance certificate(s) will be included in the investigator file. By signing the Clinical Investigation Plan, all the investigators and co-investigators involved declare to be covered by liability insurance in case of an adverse event due to medical error occur during the Zenith® Dissection investigation.

